5.3 Preparation and Administration of Study Drug

Pregabalin will be dispensed by the HUP investigational pharmacy. Study subjects will self-administer the medication orally following the indicated scheduling.

5.4 Subject Compliance Monitoring

5.4.1 Study subject non-compliance will be defined by any of the following:

1. Failure of the study subject to complete the baseline quality of life questionnaire.

- 2. Failure of the study subject to take at least 75% of prescribed pregabalin dosage for at least 4 weeks.
- 3. Failure of the study subject to receive at least 70% of prescribed radiation treatments.

5.4.2 Study subject compliance monitoring will consist of:

- 1. Documentation that the study subject has completed the baseline quality of life questionnaire.
- 2. Documentation that the study subject has taken at least 75% of prescribed pregabalin dosage for at least 4 weeks.
- 3. Documentation that the study subject has received at least 70% of prescribed radiation treatments.

5.5 Prior and Concomitant Therapy

Patients participating in the trial will *not* be allowed to use extra virgin olive oil in therapeutic doses and will be discouraged from using NSAIDS during the trial. Patients are encouraged not to take NSAIDS due to the risk of masking a fever associated with aspiration pneumonia. A single dose may be taken on an occasional basis after ensuring they are afebrile. Given the risk of neutropenia, and an increased risk of aspiration pneumonia in this population (secondary to radiation-induced dysphagia), we recommend that patients not take NSAIDS or Tylenol during the course of treatment, as this may mask a fever and delay diagnosis of febrile neutropenia, a condition that requires timely diagnosis and treatment. Please note this is the standard practice for head and neck patients treated in Radiation Oncology at the Hospital of the University of Pennsylvania. We ask patients to refrain from taking NSAIDS for the reasons noted above, however, patients are not allowed to suffer, with consultation from the treating physician/NP, concessions may be made for a single dose to manage symptoms such as a headache. In the event of more severe pain, patients are offered opioids. We would like to stress that our goal is pain management and thus, have, as part of standard practice, many options to offer patients that will not interfere with this study. There are no dietary limitations for extra virgin olive oil. Viscous Lidocaine or steroids can be used, but will be documented as possible confounders in results.

6 Study Procedures

6.1 Screening

The informed consent and HIPAA consent form will be reviewed with the patient and the appropriate signatures will be obtained. Prior to receiving first radiation treatment, prospective study subjects will be screened for eligibility by a physician/NP and research coordinator. The eligibility checklist will be completed (see Appendix B). Patients must have a CBC and blood chemistry panel within the preceding 30 days prior to screening for eligibility demonstrating appropriate creatinine clearance and platelet counts and delineated in the exclusion criteria and on the eligibility checklist. Patients may also be consented and screened following the first radiation treatment so long as they will be able to start the Pregabalin or matching placebo before the end of the 2nd week of radiation treatment.

6.2 Baseline

During a routine clinic visit prior to receiving first dose of Pregabalin or matching placebo, the subject will complete the validated quality of life questionnaire (see Appendix C), the validated pain assessment (see Appendix D) and the Depression Screening (see Appendix H). The validated toxicity assessment form (see

Appendix E) will be completed with the subject by a physician/NP or designee in the Department of Radiation Oncology. This assessment will be performed within 4 (four) weeks of initiation of treatments, for example at the time of planning simulation or treatment set-up.

Page 16

6.3 On Treatment Visits

Subjects will be instructed to begin taking the study drug on the first day of radiation treatment (or if applicable – on a day following the first radiation treatment up through the end of the 2^{nd} week of radiation treatment). On a weekly basis, the subject will be provided with an adequate supply of study drug and will be given instructions on details of administration in accordance with the assigned study cohort and treatment regimen (see Sections 3.1 and 5.2).

During each routine weekly on treatment visit (or another day weekly while on treatment), the subject will complete the validated oral mucositis questionnaire (OMQ) (see Appendix F), the pain assessment, the Depression Screening and the quality of life questionnaire. In addition, the pain diary and the pill diary will be collected from the patient for the corresponding week. The physician/NP or designee will complete the toxicity assessment form with the subject. If subjects require additional on treatment visits in addition to the routine weekly visit, no study documentation is required unless there is an adverse event, in which case the appropriate procedure will be followed as outlined in Section 8.

During titration, patients will be screened daily by designated study staff before or after their daily radiation treatment in order to discuss/report with/to the PI any potential adverse events associated with the study drug. In addition, during titration patients will be screened for suicidal ideation by designated study staff before or after their daily radiation treatment. All patients will be screened using the Depression Screening assessment (appendix H). For patients scoring a 10 or higher or reporting anything other than a 0 on question # 5, the procedure outlined in Section 5.2 will be followed.

6.4 Follow up Visit

During the routine approximate one-month inspection follow-up visit, the subject will complete the OMQ, pain assessment, the Depression Screening and the quality of life questionnaire. The pain diary will be collected for the corresponding time frame. The physician/NP or designee will complete the toxicity assessment form with the subject. This visit will occur approximately 4 weeks post completion of the final radiation treatment, but may occur no less than 3 and no more than 6 weeks post completion of radiation treatment.

Version 06-01-2015 6.5 Schedule of Events

Study Procedures

				Follow up
	Eligibility	Baseline	Weekly during treatment	(approximately 1 month)
Tests and Laboratory				
History and PE	Х			
CBC and blood chemistry panel	X*		Х	
Assessments				
Depression Screening Form		Х	Х	X
Quality of Life Questionnaire		Х	Х	X
Pain Assessment Form		Х	Х	X
Toxicity Assessment Form/Adverse Events		X**	Х	Х
Oral Mucositis Questionnaire (OMQ)			Х	X
Pain Diary			Х	X
Study Drug				
Study drug dispensing			X***	X****
Pill Diary/Study drug compliance			Х	X

*with 30 days prior to eligibility check

** must be completed within 4 weeks of start of Pregabalin or matching placebo treatment

*** starting on first day of radiation treatment (or if applicable – starting any day following the first radiation treatment up through the end of the second week of radiation treatment)

****as needed to begin study drug taper

7 Statistical Plan

7.1 Hypothesis

In head and neck cancer patients treated with chemoradiotherapy, we expect that pregabalin will lessen mucositis-related pain which will translate into a reduced cumulative opioid dose and as a result, will improve quality of life.

7.2 Design

This is a 2 arm *double blind* randomized pilot trial to generate preliminary data on the cumulative opioid dose for head and neck cancer patients treated with either placebo (the control arm) or Lyrica (pregabalin). To reduce bias in terms of initiation of opioid treatment and dosage prescribed, neither the patient, the study coordinator, nor the treating physician/nurse practitioner will know whether Lyrica or placebo had been assigned to a patient. The cumulative opioid dose over an 11 week observation period will be recorded. Randomization will eliminate selection bias and balance patient factors between arms. Ten patients will be enrolled on each arm for a study total of 20 patients. Study drug will be taken daily during the approximately 7 weeks of radiotherapy and for 4 additional weeks post-radiotherapy. The primary choice of the opioid drug for this study is oxycodone.

7.3 Objectives

The primary objective is to generate preliminary data on the cumulative opioid dose over the 11 week observation period for head and neck cancer patients treated with either placebo (the control arm) or Lyrica. Secondary objectives are to generate preliminary data on mucositis pain and quality of life.

7.4 Endpoints

d as the sum of opioid dose x duration in days over the observation

Page 18

Cumulative opioid dose will be computed as the sum of opioid dose x duration in days over the observation period (approximately 7 weeks of treatment and then 1 month post-treatment). Mucositis pain will be measured using two self reported questions found in the Oral Mucositis Questionnaire (OMQ). Quality of life is self reported using an EORTC questionnaire. These outcomes will be scored on day 1 of radiation, then weekly during 7 weeks of radiation and then at 1 month post-radiation.

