1.1 Background

Patients undergoing radiation therapy (RT) for malignancies of the head and neck almost invariably develop painful oral mucositis, which may result in decreased oral intake, weight loss, and treatment interruptions [1, 2]. Altered fractionation and concomitant chemotherapy are now commonly utilized, as they have demonstrated improved outcomes, but are complicated by increased toxicity, including mucositis [3-6].

It is now clear that a successful outcome with RT is critically dependent on the ability to manage and support a patient's acute symptoms without necessitating treatment interruptions. This time dependence has been shown to be offset by increasing the total radiation dose suggesting that this may reflect the impact of tumor cell repopulation [7].

From a clinical perspective, symptomatic mucositis accounts for a large proportion of radiotherapy treatment interruptions [8, 9]. Studies have also demonstrated that mucositis pain (MP) is a significant reason for increased rated of hospitalization and treatment costs. These retrospective findings have recently been confirmed in a prospective study [10]. These findings underscore the importance of developing more effective strategies to manage symptomatic mucositis. While ongoing efforts continue to study the biology of radiation mucositis in hopes of developing effective selective mucosal radiation protectants, no effective agents exist for clinical management [11, 12]. In fact, a disproportionate amount of effort has been devoted towards the development of agents that prevent or reduce the pathogenesis of radiation induced mucositis (RIM) rather than optimizing current symptomatic management paradigms.

The current standard of care for management of MP associated with RIM is topical analgesics and oral pain medications including opioids when necessary [13]. While effective at managing pain, the use of morphine and its derivatives is associated with multiple side effects, including depression, sedation, nausea, vomiting, constipation, itching, potential addition, and respiratory depression. Additionally, certain pain types are less responsive to opioid analgesia, requiring increasingly higher doses and additional side effects. Neuropathic pain, for example, is one pain type where opioid use is typically recommended only as a second-line agent [14].

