1.4 Dose Rationale and Risk/Benefits

The recommended dose of pregabalin ranges from 150 mg/day to 600 mg/day divided into twice or three times daily doses. Increasing dose above 300 mg/day appears to correlate with increasing side effects including dizziness, somnolence, blurry vision, peripheral edema, and constipation. It appears that incremental benefits in neuropathic pain are smaller at the higher dose levels.

2 Study Objectives

Primary Objective

To assess the effectiveness of pregabalin in decreasing the cumulative dose of opioid used in the management of mucositis pain related to radiation therapy to the head and neck.

Secondary Objectives

To assess for quality of life and level of mucositis pain among subjects treated with pregabalin in conjunction with radiation therapy to the head and neck.

To compare the effects of pregabalin in decreasing the need for and degree of opioid use, quality of life, and level of mucositis pain in these patients.

3 Study Design

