3.4 Primary Study Endpoints

Total opioid use as recorded at weekly on-treatment visits and follow-up visit. Patients will keep a diary of opioid use at home during the week. The diary will be collected by the staff and recorded at the weekly visit.

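### Does the cumulative opioid endpoint need a stated unit and a named source for inpatient doses?

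*Combined protocol and SAP*

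**What the plan says.** The primary objective in section 2 concerns "decreasing the cumulative dose of opioid used in the management of mucositis pain". Section 7.4 makes it operational: "Cumulative opioid dose will be computed as the sum of opioid dose x duration in days over the observation period". No section states a unit, an equivalence or a conversion table.

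On the drug, section 7.2 says: "The primary choice of the opioid drug for this study is oxycodone". Section 5.5 is more general: "In the event of more severe pain, patients are offered opioids".

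On the source, section 3.4 gives the endpoint as "Total opioid use as recorded at weekly on-treatment visits and follow-up visit", then adds: "Patients will keep a diary of opioid use at home during the week". The Appendix F diary has a column for the medicine and the amount taken. The Appendix E questionnaire asks patients who took pain medication to list it, for the preceding 24 hours only. Section 9.2 names hospital records, pharmacy dispensing records and patient diaries among its examples of source data, and requires missing data to be explained.

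On use, section 7.5 reports a mean and standard deviation per arm to inform the design of a later trial. It rules out inferential analysis.

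**The concern.** A sum of doses has a meaning only if the doses share a unit. Oxycodone is preferred but not exclusive, so a patient could take a second opioid, or another route of different potency. The formula does not say how to add it, and two analysts could derive different totals from the same diary.

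The second gap is coverage. The background in section 1.1 says "mucositis pain (MP) is a significant reason for increased rated of hospitalization and treatment costs", so admissions are foreseeable, and a diary of home use would not be expected to hold doses given on a ward.

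The pilot's main product would be at stake. Section 7.6 says no data exist for these patients, so the mean and standard deviation from this study would go straight into the next trial's sample size. An error of scale there would not show in any reported interval.

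**Working it through.** **Figures in the plan.** The plan gives no standard deviation, effect size, alpha or power, so there is no sample size calculation to reproduce. The simple arithmetic agrees: 10 x 2 = 20 patients, and 7 + 4 = 11 weeks = 77 days. The follow-up window in section 6.4 (3 to 6 weeks after radiotherapy) gives 49 + 21 = 70 to 49 + 42 = 91 days.

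**Can the total be put on one scale from what is collected?**
- Drug and amount: the Appendix F diary asks for both. It is collected weekly on treatment and again at follow-up (sections 6.3, 6.4).
- Cross-check on drug name: Appendix E covers (7 + 1) days out of 77 = 10.4%. That is enough to check which drug is used, but not to supply the total.
- Inpatient doses: section 3.4 sets total use as the endpoint and does not limit it to home use. Section 9.2 accepts hospital records as source data.

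The raw material is therefore largely there. What is unwritten is the conversion convention.

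**Size if doses were added unconverted.** All inputs here are assumed: an arm of 10, lognormal totals with mean 3000 mg and SD 1500 mg, and half of an affected patient's dose given as another opioid with potency r relative to oxycodone. The recorded total is then multiplied by 1 + 0.5(1/r - 1):
- r = 0.67: 1.246
- r = 1.5: 0.833
- r = 4: 0.625

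With k patients affected at random, the expected shift in the mean is (k/10) x (multiplier - 1). For k = 2 this is 0.2 x 0.246 = +4.9% and 0.2 x (-0.375) = -7.5%. Results from 200,000 simulated arms, for r = 0.67 / 1.5 / 4:

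| Affected of 10 | Change in mean (%) | Change in SD (%) |
|---|---|---|
| 1, random | +2.5 / -1.7 / -3.7 | +3.8 / -1.0 / -0.2 |
| 2, random | +4.9 / -3.3 / -7.5 | +7.3 / -2.1 / -1.1 |
| 3, random | +7.4 / -5.0 / -11.3 | +10.4 / -3.4 / -2.7 |
| 2 heaviest users | +8.4 / -5.7 / -12.7 | +33.2 / -19.8 / -38.0 |

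For scale, the standard error of the arm mean is 1500/sqrt(10)/3000 = 15.8%. The normal-theory 95% interval for an SD from 10 patients runs from sqrt(9/19.02) = 0.69 to sqrt(9/2.70) = 1.83 times the estimate.

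**Size if an admission were missed.** At a constant daily dose, 7 lost days are 7/91 = 7.7%, 7/77 = 9.1% or 7/70 = 10.0% of that patient's total. With 2 of 10 admitted (assumed), the arm mean loses 1.5%, 1.8% or 2.0%. The loss is larger if ward doses exceed home doses.

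**The case for a change.** The best case for a change is that this is the primary endpoint and the remedy is short. Sampling error is reported and a scale error is not, so being smaller than the standard error does not excuse it. The patients who change drug may also be those in most pain. In the heaviest-user row the SD ratio runs from 1.33 to 0.62. At a fixed difference, the next trial's sample size would then be multiplied by 1.33^2 = 1.8 or 0.62^2 = 0.4. A more extreme assumption, with one patient's whole total recorded at five times its equivalent (mean 100, SD 50), raises the SD to 126.5 and the sample size by (126.5/50)^2 = 6.4.

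The gap in wording is real, and unconverted addition could matter. But all of these figures assume that someone adds milligrams of unlike opioids as they stand, and no section directs that. Conversion removes the effect apart from the approximation in the ratios. The five-fold case also lies far outside the 0.625 to 1.246 range used above.

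The evidence that several opioids are in use is thin. The remark in section 1.1 that "the use of morphine and its derivatives is associated with multiple side effects" is a general comment on opioid toxicity. The sentence before it, which does describe standard care, speaks of topical analgesics and oral pain medication, including opioids when needed.

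On admissions, adverse event reports cannot be relied on to find them all, because section 8.2 leaves toxicity of radiotherapy and chemotherapy unrecorded. Other safeguards remain. This is a single centre where patients attend for daily radiotherapy, diaries are collected at each weekly visit, and section 9.2 requires missing entries to be explained. An admission should show up as a gap that staff must account for.

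There is also the worry that a table chosen after unblinding could be chosen to suit the result. With no test planned, there is little to gain from such a choice.

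**Conclusion.** The plan leaves a convention unwritten, and an analyst would fill it sensibly. Nothing in the documents shows that unlike opioids will be added unconverted or that ward doses will be left out. The diary holds drug and amount, and hospital records are admissible for the few stays that may occur.

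The true size cannot be known from the documents. Under the assumed random case with up to 3 of 10 patients affected and no conversion, the arm mean shifts by at most 11.3% and the SD by at most 10.4%, both within sampling error for 10 patients. Missed 7-day admissions in 2 of 10 cost about 2% of the mean. The larger SD shifts need both unconverted addition and the heaviest users to be the ones affected. Patients on oral oxycodone at home throughout are not touched at all.

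The judgement rests on this being a descriptive pilot of 20 patients with one preferred opioid and recoverable raw data. A confirmatory trial testing the same endpoint would be a different matter.

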7.5 Data Analyses

For each arm, the mean and standard deviation of the cumulative opioid dose will be computed. In addition, the number of patients who drop out prior to the end of the 11 week observation period will be noted. For each arm, the mean and standard deviation of the mucositis pain and quality of life scores will be computed at each time point. Descriptive analyses of the mean and SD of the cumulative opioid dose and the number of incomplete dropouts, will inform the design of a future randomized trial to test the hypothesis that Lyrica will significantly decrease the cumulative opioid dose over the 11 week observation period. No inferential analyses are intended in this study.

7.6 Sample Size Justification

There is presently no data for head and neck patients. A total of 20 patients (10 per arm) will be sufficient to generate preliminary data on the primary and secondary endpoints. Study enrollment should be completed in 1 year. Follow-up will continue for an additional 2.5 months.

7.7 Subject Populations for Analysis

We will analyze the all-treated population and any subject enrolled into the study that received at least one dose of study drug. Any patient who was randomized and then withdrew consent prior to receiving study drug will be replaced. The number of patients who drop out prior to the end of the 11 week observation period will be noted but these patients will be included in the analysis population.

8 Safety and Adverse Events

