4.3.1 Vulnerable Populations

Children, pregnant women, fetuses, neonates or prisoners are not included in this research study. Women of childbearing potential must be non-pregnant and non-lactating and willing to exercise an effective form of birth control during radiation therapy (e.g. oral contraceptive, IUD, condoms or other barrier methods etc.). Before receiving chemoradiation, female patients must have a negative pregnancy test. Hysterectomy or menopause must be clinically documented.

Early Withdrawal of Subjects

When to Withdraw Subjects

- 1. At the subject's request.
- 2. Determination by the investigator that it is no longer safe for the subject to continue therapy.
- 3. The presence of CTCAE Grade 4-5 toxicity possibly, probably or definitely related to the study drug.

How to Withdraw Subjects

1. If pregabalin has not been administered, the study subject will proceed to receive the recommended RT.

2. If pregabalin has been administered, the study subject will taper the dose gradually over a minimum of one week at the discretion of the treating physician/NP.

Data Collection and Follow-up for Withdrawn Subjects

Even though subjects may be withdrawn prematurely from the study, it is imperative to collect at least survival data on such subjects throughout the protocol defined follow-up period for that subject (though careful thought should be give to the full data set that should to be collected on such subjects to fully support the analysis). Such data is important to the integrity of the final study analysis since early withdrawal could be related to the safety profile of the study drug. If a subject withdraws consent to participate in the study:,

- If the patient withdraws consent, s/he will be given the choice of withdrawing completely meaning no further contact or data collection or giving the research team permission to follow up contact for data collection. It must be a high priority to try to obtain at least survivial data on all subjects. Patients that agree to be followed with be asked to sign to sign the 'Consent to Follow up' form (appendix G).
- If the PI, treating oncologist or physician withdraws the patient for any reason, the patient will be given the same choice as subjects who withdraw consent themselves. Patients agreeing to be followed with also sign the 'Consent to follow up.'

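### Patients who leave before week 11 stay in the analysis of cumulative opioid dose, but no rule says what their shortened totals contribute

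*Combined protocol and SAP*

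**What the plan says.** Section 7.2 sets the window: "The cumulative opioid dose over an 11 week observation period will be recorded". Section 7.4 gives the formula: "Cumulative opioid dose will be computed as the sum of opioid dose x duration in days over the observation period", the period there being about 7 weeks of treatment and then 1 month. Section 7.5 gives the summary: "For each arm, the mean and standard deviation of the cumulative opioid dose will be computed". It adds a count of early leavers and says that the mean, the SD and "the number of incomplete dropouts, will inform the design of a future randomized trial". Section 7.7 analyses everyone who took at least one dose, and on early leavers it reads: "drop out prior to the end of the 11 week observation period will be noted but these patients will be included in the analysis".

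The text on withdrawn subjects (after section 4.3.1) says that "it is imperative to collect at least survival data on such subjects throughout the protocol defined follow-up period". It adds that "careful thought should be give to the full data set that should to be collected on such subjects", without naming opioid use. Patients who withdraw, or whom the investigator or a treating physician withdraws, may choose between no further contact and "giving the research team permission to follow up contact for data collection", using the form in Appendix G.

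Section 9.2 has staff recontact patients about blank items and mark unobtainable answers as missing. That governs source documents, not the analysis.

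**The concern.** Section 7.7 settles who is analysed. It does not settle what number a patient who left in, say, week 4 contributes: the partial sum, a scaled or imputed value, or nothing. Taken literally, 7.4, 7.5 and 7.7 together put the partial sum into the mean as if it covered 11 weeks. Two analysts could report different primary results from the same diaries.

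Early exit is foreseeable. Section 5.2 removes patients on the depression screen, section 8.1 removes those whose GFR falls below 30, and the withdrawal text removes those with related Grade 4-5 toxicity. Drug-related exits could differ between arms.

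At stake are the planning figures for the next trial, which are this pilot's stated product. The dropout count shows how many totals are short, but not by how much.

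**Working it through.** **The plan's own figures.** 10 + 10 = 20 patients and 7 + 4 = 11 weeks (77 days) both check. Section 7.6 gives no SD, precision or dropout rate, so there is nothing further to reproduce.

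**Direction.** Daily dose cannot be negative, so a sum stopped early cannot exceed the full 11-week sum. If recorded sums are used and nobody is counted beyond day 77, the arm mean is at or below the true mean. A patient whose diary continues after exit, or who would have used no opioid afterwards, adds no error.

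**Assumed inputs.** The documents give no dropout rate, opioid profile or coefficient of variation (CV). I assume:
- a late weekly profile of 0, 0, .2, .4, .6, .8, 1, 1, .8, .6, .4 of peak (sum 5.8), or a flat one
- exit equally likely at the end of weeks 1 to 10
- dropout share d, with m the share of the 11-week total used before exit

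For the late profile, m after weeks 1 to 10 is 0, 0, .034, .103, .207, .345, .517, .690, .828, .931, so E[m] = 0.366. For the flat profile m = k/11, so E[m] = 0.50.

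**Mean, exit unrelated to need.** Mean as recorded ÷ true mean = 1 − d(1 − E[m]).
- d = 0.20, late: 1 − 0.20 × 0.634 = 0.873, or 12.7% low. Flat: 1 − 0.20 × 0.50 = 0.900, or 10.0% low.
- Exit only in weeks 1-3: 19.8% low (flat 16.4%). Exit only in weeks 8-10: 3.7% low (flat 3.6%).
- One average leaver in 10 lowers the mean by 10% × (1 − m): 10% after week 1, 4.8% after week 7, 0.7% after week 10 (flat 9.1%, 3.6%, 0.9%).

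**Arm comparison with no drug effect.** Dropout of 20% on pregabalin and 10% on placebo: 1 − 0.873/0.937 = 6.8% apparent reduction (flat 5.3%). With 30% and 10%: 1 − 0.810/0.937 = 13.5% (flat 10.5%). Equal dropout gives 0. Reversing the arms reverses the sign.

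**SD as recorded ÷ true SD**, exit unrelated to need: √{(1 + CV²)[(1 − d) + d·E(m²)] − [1 − d(1 − E[m])]²} ÷ CV, with E(m²) = 0.247 (late). At d = 0.20 and CV 0.8: √(1.64 × 0.849 − 0.762) ÷ 0.8 = 0.99.

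| CV | Change in SD, late profile, d = 0.20 |
|---|---|
| 0.3 | +35% |
| 0.5 | +9% |
| 0.8 | −1% |
| 1.0 | −3% |

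**Bias of the mean by handling rule.** Simulation of 60,000 arms of 10: lognormal totals, CV 0.80, late profile, 20% exit. Exit is unrelated to need, or its log-odds rise or fall by 1 per SD of log total. RMSE is in brackets, as a fraction of the true mean.

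| Rule | Unrelated | High users leave | Low users leave |
|---|---|---|---|
| Totals as recorded | −13% (0.28) | −20% (0.29) | −8% (0.28) |
| Short totals set to missing | 0 (0.29) | −14% (0.27) | +10% (0.32) |
| Sum of weekly means | 0 (0.27) | −8% (0.24) | +6% (0.28) |

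**Scale.** The SE of a full-data arm mean at CV 0.80 is 0.80/√10 = 0.253, about twice the 12.7% bias. At CV 0.3 it is 0.095, which is below that bias.

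**Visit window.** Section 6.4 allows the follow-up visit 3 to 6 weeks after radiotherapy. At 3 weeks the diary ends at day 49 + 21 = 70, leaving 7 of 77 days uncollected: 1 − 5.4/5.8 = 7% of the dose (flat 9%). The plan does not say how those days count.

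**The case against.** A reader might infer that the arm mean can only be too low. The documents do not support that without conditions. They never say to sum whatever was recorded, and section 9.2's practice of marking data as missing sits awkwardly with counting unrecorded days as zero. If short totals are treated as missing, the simulation gives 0, −14% or +10%. The one-sided result also needs a strict 77-day cut. The 11-week period is stated and the Appendix F diary has a row for each day, so a late visit need not lengthen a total. But 7.4 words the period approximately, and the visit may fall at week 13. If every completer were summed to 13 weeks at a flat dose, with leavers exiting at week 4, the arm mean would be 0.8 × 13/11 + 0.2 × 4/11 = 1.02 of the truth at 20% dropout, and 1.10 at 10%. This objection stands, and the direction is therefore stated conditionally.

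The plan also covers part of the ground. It keeps patients who cannot hold the goal dose on study (5.2), offers contact after withdrawal, sets survival only as a minimum, and reports the dropout count beside the mean. That narrows the gap to two things: opioid use is not named, and no summary rule is given.

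The remedy's gain is modest. At CV 0.80 its RMSE is better in two cases and about level when low users leave. At CV 1.0 it brings no gain when exit is unrelated to need (about 0.33 for both) and is worse when low users leave (0.36 against 0.33). Weekly means are one reasonable rule among several.

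Finally, this is a descriptive pilot with no inferential analysis. That stands, and it sets the severity.

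**Conclusion.** The gap is real and minor. No section says how an opioid total cut short by early exit enters the arm summaries. Read literally, the plan averages it as an 11-week total. Over a fixed 77-day window the mean is then at or below the truth, by about 10 to 13% at an assumed 20% dropout spread over weeks 1 to 10 and unrelated to need. The true size is unknown.

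Two further inferences are not supported. One is that the pilot will show a spurious benefit: that needs more exit on pregabalin, and no document gives a dropout rate for either arm. The other is that the SD will be biased in a known direction: it runs from +35% to −3% across CVs of 0.3 to 1.0.

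Confidence is high that the rule is missing, and lower on direction and size. The harm is confined to the planning figures for the next trial.

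**What to change.** 1. In the text on withdrawn subjects, name opioid use through week 11 as data to collect from every treated patient who stops study drug or is withdrawn and permits contact (Appendix G).
2. In 7.5, state that a total truncated by early exit is not entered as an 11-week total. One workable rule: each arm's 11-week mean is the sum of weekly means among patients observed that week, with weeks observed listed per patient and the as-recorded mean shown beside it.
3. In 7.5, report the SD for complete totals and for totals as recorded, both labelled as subject to dropout. Neither is unbiased in general.
4. In 7.4, fix the window at 11 weeks: later diary days are not counted and uncollected days are treated as missing.

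Step 1 matters most. If diaries are recovered from half of the leavers (CV 0.80, late profile, 20% dropout), the bias of the weekly-means estimate falls to 0, −4% or +3% in the three exit cases.

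The cost is a few sentences and continued diaries for a few patients, with no new instrument and no extra enrolment. The SE of the mean rises slightly (0.27 against 0.25 of the true mean at CV 0.80). Some bias remains if exit depends on opioid need. At a CV of about 1.0, no general RMSE gain should be expected. Weekly means give no per-patient total, which is why the SD has to be reported separately under step 3.
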